6.12 Safety Analysis

The safety and tolerability of the study drugs are determined by reported AEs, physical examinations, ECGs, vital signs, and laboratory tests. Unless otherwise specified, safety analyses will be based on the safety data collected for the first assigned therapy. For those subjects in the vorinostat arm who cross over to KW-0761 treatment arm, the safety data collected during the crossover portion will be presented separately.

All safety summaries will be based on the entire Safety Analysis Set.

6.12.1 Adverse Events

For subjects in the KW-0761 arm and subjects in the vorinostat arm who do not cross over to KW-0761, treatment-emergent adverse events (TEAEs) during the randomized treatment period are defined as adverse events with an onset date/time after the first dose of randomized study drug until 90 days after the last dose of randomized study drug or initiation of an alternative therapy whichever comes first.

For subjects in the vorinostat arm who cross over to KW-0761 treatment arm, TEAEs during the randomized treatment period are defined as adverse events with an onset date/time after the first dose of randomized study drug and prior to the start of KW-0761. An adverse event with onset date/time after the start of KW-0761 will also be considered as a TEAE during the randomized treatment period if it is considered related to vorinostat. TEAEs during the crossover portion are defined as adverse events with an onset date/time after the first dose of KW-0761 and within 90 days after the last dose of KW-0761 or initiation of an alternative therapy whichever comes first.

TEAEs during the randomized treatment period will be summarized by treatment arm and in total based on the Safety Analysis Set. For subjects who are initially assigned to vorinostat arm and are crossed over to KW-0761 arm, TEAEs during the crossover portion will be summarized separately. A drug-related AE is defined as any event with a relationship to study drug recorded as “definitely”, “probably” or “possibly”. Any adverse events for which relationship to study drug are not recorded will be assumed to be probable.

An overview of adverse events for the randomized treatment period will be provided which summarizes the subject incidence of the following information:

- Any AEs,
- Any TEAEs,
- Drug-related TEAEs,
- NCI/CTCAE grade III/IV/V AEs,
- NCI/CTCAE grade III/IV/V TEAEs,
- Drug-related NCI/CTCAE grade III/IV/V TEAEs,
- Deaths,
- Serious AEs,
- Treatment-emergent SAEs,
- Drug-related treatment-emergent SAEs,
- Discontinuation due to AEs,
- Discontinuation due to TEAEs, and

- Discontinuation due to drug-related TEAEs.

The number and percentage of subjects with TEAEs during the randomized treatment period will be summarized for each treatment arm and in total by system organ class (SOC) and preferred term. Drug-related TEAEs, grade III/IV/V TEAEs, and drug-related grade III/IV/V TEAEs, treatment-emergent SAEs, drug-related treatment-emergent SAEs, TEAEs leading to discontinuation of study drug, and drug-related TEAEs leading to discontinuation of study drug will be summarized in the same manner. For these summaries, subjects with multiple adverse events will be counted only once per SOC and preferred term.

In addition, summaries will be provided for the number and percentage of subjects with TEAEs and drug-related TEAEs by SOC and preferred term and by the highest NCI CTCAE grade. For these summaries, subjects with multiple adverse events will be counted only once by the highest NCI CTCAE grade within an SOC and preferred term.

Adverse events during the crossover portion that are related to KW-0761 will be summarized separately in the same manner as described above for subjects who are randomized to vorinostat arm and then crossed over to KW-0761 treatment. Another summary of adverse events related to Vorinostat may be presented if necessary.

A summary will be provided for the number and percentage of subjects with TEAEs related to KW-0761 by SOC and preferred term for all subjects exposed to KW-0761 and separately for subjects who are initially randomized to KW-0761 and for subjects who are crossed over to KW-0761 treatment.

The number and percentage of subjects with TEAEs during the randomized treatment period will also be summarized for each treatment arm and in total by system organ class (SOC) and preferred term for the following subgroups: Gender and Age (< 65 years vs \geq 65 years).

In addition to the summaries described above, exposure-adjusted incidence rate and exposure-adjusted event rate will be summarized for each treatment arm and in total by preferred term for the following special TEAEs (system organ class):

- Infections and infestations,
- Respiratory, thoracic and mediastinal disorders,
- Renal and urinary disorders,
- Musculoskeletal and connective tissue disorders.

The exposure-adjusted incidence rate per patient-months of exposure will be calculated as (the number of patients with AEs/sum of days at risk for AEs) * 30.42 days/month; the

exposure-adjusted event rate per patient-months of exposure will be calculated as (the number of AEs/sum of days at risk for AEs) * 30.42 days/month.

Listings will be provided for SAEs, grade III/IV/V AEs, and AEs leading to discontinuation of study drug and AEs leading to death. All adverse events will be listed by subject.

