5.3 Cross-over to Study Drug KW-0761

Subjects who have received 2 full treatment cycles and demonstrate progression of disease on treatment with vorinostat at the 8 week (Cycle 2, Day 26-28) assessment, or anytime thereafter, may cross over to treatment with KW-0761 after discussion with Medical Monitor or designee and receipt of approval for cross over from KKD. Investigators should strive to maintain subjects on treatment for at least the 8 week period, adjusting the dose of vorinostat as needed for toxicities in order to allow sufficient time to see effect. In cases where a subject's disease progresses rapidly (i.e., prior to 8 weeks), the Medical Monitor or designee should be contacted and may consider the possibility of early crossover, if appropriate for that subject. All subjects must undergo the full extent of disease evaluations (including CT scanning) to document PD prior to crossover.

There must be at least 2 weeks between the last dose of vorinostat and first dose of KW-0761. Subject must continue to meet eligibility criteria outlined in Section 3.4 and all toxicity must have resolved to Grade \leq 1 or to baseline in order to receive KW-0761. Treatment with KW-0761 should commence with procedures outlined for Day 1 in Table 1 of Study

Procedures for the first treatment cycle. In cases where a subject's disease progresses rapidly, the Medical Monitor or designee should be contacted and may consider initiation of treatment with KW-0761 prior to the 2-week washout period.

For subjects who are unable to tolerate the toxicities associated with vorinostat treatment, dose reduction should be initiated in an attempt to have the subject complete 2 full cycles of treatment. If the subject is unable to tolerate treatment with vorinostat despite attempts at dose reduction and has not had documented disease progression, the subject may receive KW-0761 after consultation with the Medical Monitor or designee and subsequent approval documentation from the Sponsor.

Drug intolerance is defined as:

- A serious AE attributed to the drug;
- \geq Grade 3 AEs excluding inadequately treated nausea, vomiting and diarrhea and alopecia.

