Note: Percentage is calculated using the number of subjects in the column heading as the denominator.

* 95% CIs are obtained from SAS proc lifetest using loglog transformation.

** Hazard ratio and 95% CI are based on Cox proportional hazards model with treatment, disease type, disease stage, and region as factors. P-values is obtained from a stratified log rank test with disease type, disease stage, and region as the stratification factors.

*** Kaplan-Meier estimate.

Table 14.3.1.1
Overview of Adverse Events During Randomized Treatment Period
Safety Analysis Set

Adverse Event Category	Vorinostat N=xx		KW-0761 N=xx	
	n	(%)	n	(%)
Adverse Events (AEs)				
Any AEs	xx	(xx.x)	xx	(xx.x)
Any TEAEs	xx	(xx.x)	xx	(xx.x)
Drug-related TEAEs	xx	(xx.x)	xx	(xx.x)
NCI/CTCAE Grade III/IV/V AEs				
Any Grade III/IV/V AEs	xx	(xx.x)	xx	(xx.x)
Any Grade III/IV/V TEAEs	xx	(xx.x)	xx	(xx.x)
Drug-related Grade III/IV/V TEAEs	xx	(xx.x)	xx	(xx.x)
Deaths	xx	(xx.x)	xx	(xx.x)
Serious Adverse Events (SAEs)				
Any SAEs	xx	(xx.x)	xx	(xx.x)
Treatment-emergent SAEs	xx	(xx.x)	xx	(xx.x)
Drug-related Treatment-emergent SAEs	xx	(xx.x)	xx	(xx.x)
Discontinuation Due to AEs				
Any AEs	xx	(xx.x)	xx	(xx.x)
Any TEAEs	xx	(xx.x)	xx	(xx.x)
Drug-related TEAEs	xx	(xx.x)	xx	(xx.x)

Note: Percentage is calculated using the number of subjects in the column heading as the denominator.

Table 14.3.1.2
 Number (%) of Subjects with Treatment-Emergent Adverse Events (TEAEs) During Randomized Treatment Period
 By System Organ Class and Preferred Term
 Safety Analysis Set

System Organ Class* Preferred Term*	Vorinostat N=xx		KW-0761 N=xx	
	n	(%)	n	(%)
Subjects with Any TEAEs	xx	(xx.x)	xx	(xx.x)
System Organ Class 1	xx	(xx.x)	xx	(xx.x)
Preferred Term 1	xx	(xx.x)	xx	(xx.x)
Preferred Term 2	xx	(xx.x)	xx	(xx.x)
System Organ Class 1	xx	(xx.x)	xx	(xx.x)
Preferred Term 1	xx	(xx.x)	xx	(xx.x)
Preferred Term 2	xx	(xx.x)	xx	(xx.x)
Etc. ...				

Note: Percentage is calculated using the number of subjects in the column heading as the denominator.
 * MedDRA Version 15.1 was used for coding.

The following table will have a similar layout as Table 14.3.1.2:

Table 14.3.1.3
Number (%) of Subjects with Drug-Related Treatment-Emergent Adverse Events (TEAEs) During Randomized Treatment Period
By System Organ Class and Preferred Term
Safety Analysis Set

Table 14.3.1.4
 Number (%) of Subjects with Treatment-Emergent Adverse Events (TEAEs) During Randomized Treatment Period

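### Between-arm TEAE percentages rest on unequal time at risk, and only four organ classes get exposure-adjusted rates, so equal toxicity per unit time can print as an excess on KW-0761

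*SAP*

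**What the plan says.** SAP 6.12.1 defines two counting windows for the randomized treatment period.

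- **KW-0761 subjects, and vorinostat subjects who do not cross over:** from first dose "until 90 days after the last dose of randomized study drug or initiation of an alternative therapy whichever comes first".
- **Vorinostat subjects who cross over:** events with "onset date/time after the first dose of randomized study drug and prior to the start of KW-0761". A later event "will also be considered as a TEAE during the randomized treatment period if it is considered related to vorinostat".

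Protocol 5.3 sets the usual interval between the two drugs: "There must be at least 2 weeks between the last dose of vorinostat and first dose of KW-0761". In rapid progression the medical monitor "may consider initiation of treatment with KW-0761 prior to the 2-week washout period".

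The tables are mostly subject counts, broken down into system organ classes (SOCs) and preferred terms. Of the main one the SAP writes: "The number and percentage of subjects with TEAEs during the randomized treatment period will be summarized for each treatment arm and in total". The same layout serves the Grade III/IV/V, SAE and discontinuation tables. The notes to Tables 14.3.1.1 and 14.3.1.2 fix the denominator: "Percentage is calculated using the number of subjects in the column heading as the denominator". Exposure-adjusted incidence and event rates are given "by preferred term for the following special TEAEs (system organ class"): infections, respiratory, renal/urinary and musculoskeletal. The footnote to Table 14.3.3.2 ends days at risk at the first KW-0761 dose for crossovers. For everyone else it uses last dose minus first dose plus 90.

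**The concern.** Two features make time at risk differ by arm. Crossover can shorten the post-dose window only in the vorinostat arm. And the design targets a 50% longer median PFS on KW-0761, so longer treatment, with more time to record an event, is to be expected there if the target is met.

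A raw percentage absorbs both. If the two drugs produced events at the same rate per day, the KW-0761 column could still show more subjects with any TEAE, a Grade III/IV/V TEAE or an SAE, and a real vorinostat excess could be masked. Further assessment of KW-0761 safety is a stated secondary objective, and these side-by-side columns are what readers will compare. The SAP adjusts for exposure in four organ classes but not in skin, gastrointestinal, blood, general or other classes, nor in any overall row. It carries no caution about the unequal windows.

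**Working it through.** **Inputs.** From the documents: median PFS 169 and 254 days (Protocol 10.3, SAP 6.3), the 90-day window, the 2-week minimum interval and 1:1 allocation. Assumed here: PFS stands in for treatment time; the event rate is constant and equal in both arms; crossover fraction, AE frequency and timing of alternative therapy are varied. The plan states no figure for any of these last three, so there is no plan figure on this point to reproduce. Its only sizing figure does reproduce from the same medians: hazard ratio 169/254 = 0.665 needs 254 events by the Schoenfeld formula, against 255 stated.

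**1. Both effects together.** Exponential treatment time has mean 169/ln 2 = 243.8 days (vorinostat) and 254/ln 2 = 366.4 days (KW-0761). Take 70% crossover at 14 days and 90-day windows otherwise.

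- Vorinostat time at risk: 243.8 + 0.7×14 + 0.3×90 = 280.6 days.
- KW-0761 time at risk: 366.4 + 90 = 456.4 days.

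With daily rate λ, mean treatment time m and post-dose window w, the proportion with an event is 1 − E[exp(−λw)]/(1 + λm). Setting vorinostat to 20% gives λ = 0.000867, since 0.9690/1.2113 = 0.800.

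| Case | Event-free on KW-0761 | KW-0761 prints |
|---|---|---|
| Longer treatment and longer window | 0.9250/1.3176 = 0.702 | 29.8% |
| Longer window only | 0.9250/1.2113 = 0.764 | 23.6% |
| Longer treatment only | 0.9690/1.3176 = 0.735 | 26.5% |

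Setting vorinostat to 40% (λ = 0.002217) gives 54.8% with both effects and 46.8% with the window alone.

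**2. The window by itself.** Fix treatment at 169 days in both arms and KW-0761 incidence at 30%, so λ = −ln(0.7)/259 = 0.001377. A crossover subject has 169 + 14 = 183 of 259 days at risk (71%), hence 1 − exp(−0.001377×183) = 22.3%.

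| Crossover | Vorinostat prints | KW-0761 excess (points) |
|---|---|---|
| 25% | 28.1% | 1.9 |
| 50% | 26.1% | 3.9 |
| 75% | 24.2% | 5.8 |

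At 50% crossover, with non-crossover vorinostat subjects still followed for 90 days, the excess depends on how many KW-0761 subjects start another therapy:

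- half at day 30: 0.8 points;
- half at day 14: 0.0 points;
- 75% at day 14: −1.9 points.

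Without alternative therapy, if the off-drug event rate is half or a quarter of the on-drug rate, 3.9 points falls to 2.3 or 1.3.

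**3. Adding treatment time back to the reversal case.** Take 50% crossover, 75% of KW-0761 subjects on other therapy at day 14, and the plan's medians as in step 1. Then 20% on vorinostat still prints as 25.0% on KW-0761, and 40% as 46.6%.

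**4. What a rate does.** In the step 2 setting at 50% crossover, mean time at risk is 259 days (KW-0761) and 0.5×259 + 0.5×183 = 221 days (vorinostat). The SAP's incidence-rate formula gives 0.300/259×30.42 = 0.0352 against 0.2614/221×30.42 = 0.0360 per patient-month. The 3.9-point excess goes. Ending time at the first event would return the true 0.001377×30.42 = 0.0419 in both arms.

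**5. A flaw not to copy.** Table 14.3.3.2 adds a flat 90 days for subjects who do not cross over, although TEAE counting stops at alternative therapy. If half of KW-0761 subjects start another therapy at day 30, the KW-0761 event rate is multiplied by (0.5×199 + 0.5×259)/259 = 0.884, an understatement of about 12%.

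**The case against.** The strongest reply is that the windows are less unequal than they look. The 90-day window also closes at alternative therapy, so a KW-0761 subject who progresses and switches is cut off much as a crossover subject is. Later events judged vorinostat-related still count for vorinostat. The protocol asks for causality against both drugs for 30 days after vorinostat stops, and the SAP treats an unrecorded relationship as probable. Two weeks is a minimum, with earlier starts by exception. All this stands: the window effect is conditional in size and sign, and the drug-related tables are largely protected from it. So are the discontinuation tables, because an event that stops the drug ordinarily begins before the last dose.

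The model is also generous. It has no data cutoff, no 12-month limit after complete response and no stopping for toxicity, and it uses PFS for treatment time. That stands too, so the figures are illustrations and not predictions.

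Finally, the AE summaries are descriptive, exposure is summarized by arm, every event is listed with dates, and four organ classes are already adjusted. This limits the harm. It does not give the reader time-adjusted overall, Grade III/IV/V, SAE or other organ-class rows, and step 3 shows that alternative therapy does not remove the part due to treatment time.

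**Conclusion.** The concern holds in a limited form. Followed exactly, the plan prints percentages over arm-dependent time at risk in the overall, Grade III/IV/V, SAE and remaining organ-class rows, with no adjusted counterpart. Under the step 1 assumptions the spurious gap is 20% versus about 30%. Roughly 6 of those 10 points come from longer KW-0761 treatment and under 4 from the window.

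A reader might infer more than the documents support:

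- **That the crossover cut-off by itself always makes equal toxicity look like excess harm on KW-0761.** At equal treatment time it can disappear or reverse, and the crossover fraction, off-drug event rate and timing of alternative therapy that decide this are not given.
- **That the tables would yield false significant differences.** SAP 6.12.1 plans no hypothesis tests on adverse events.
- **That unrelated late vorinostat events reappear in the crossover SOC tables.** Tables 14.3.2.2 to 14.3.2.6 carry only KW-0761-related events.

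The primary efficacy analysis is untouched. This is a worthwhile, inexpensive improvement to how the safety comparison can be read.

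**What to change.** In SAP 6.12.1 and the 14.3.1.x tables:

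1. Extend the exposure-adjusted incidence rate already planned for four organ classes to the overall TEAE, Grade III/IV/V and treatment-emergent SAE rows and to all remaining SOCs and preferred terms.
2. End each subject's days at risk at the first event or at that subject's own TEAE cut-off: crossover, alternative therapy, death, data cutoff or 90 days after the last dose, whichever comes first.
3. State that between-arm safety statements rest on these rates, and keep the n (%) tables as the full record.

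An overview table using one common post-dose window in both arms is an optional supplement. It would leave out late events and would not correct for treatment time, so it cannot replace the rates.

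The cost is SAP wording, extra programming of a rate the SAP already defines, and longer tables. No new data are needed.

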10.2 Analyses of Safety Data

The safety and tolerability of KW-0761 and vorinostat is determined by reported AEs, physical examinations, ECGs, vital signs, and laboratory tests. All summaries for the Safety Analysis Set will be prepared for each treatment arm. For those subjects in the vorinostat arm who cross over to KW-0761 treatment arm, AEs with an onset date/time after the first dose of KW-0761 will be summarized separately within that KW-0761 crossover group.

The World Health Organization (WHO) Drug Dictionary will be used to classify prior and concomitant medications by therapeutic class and Preferred Term. Prior medications include medications that were taken within 30 days prior to the Pre-treatment Visit. Concomitant medications include medications that started at any time and were taken at any time after the start of treatment until the end of the entire treatment period.

Adverse events are collected from the time the subject signs the ICF until 90 days after the last dose or initiation of alternative therapy, whichever comes first. In all subjects who cross over from vorinostat to KW-0761, the causality should be assessed for both drugs for 30 days after vorinostat was stopped (or later if the event is considered to be related to vorinostat). The NCI-CTCAE v4.0 system will be used to grade AEs. Treatment-emergent AEs will be grouped and tabulated by MedDRA preferred terms and system organ class. AEs will be

classified by body system, incidence, severity, and causality. All treatment-emergent AEs will be summarized showing the number and percent of subjects for each outcome.

The results from physical examination will be presented in the subject data listings. Vital sign measurements will be summarized at each time point. The incidence of clinically significant laboratory abnormalities will be presented, and laboratory data will be summarized at each time point by the NCI-CTCAE v4.0 toxicity grade. Laboratory data will be presented for subjects having Grade 3 or 4 changes from baseline by treatment arm.

Pre- and post-treatment serum samples will be assayed for development of human antibodies to KW-0761 (anti-KW-0761).

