Table 14.3.1.13	Number (%) of Subjects with Treatment-Emergent Adverse Events (TEAEs) During Randomized Treatment Period – By Age Group, System Organ Class and Preferred Term – Safety Analysis Set
Table 14.3.2.1	Overview of Adverse Events During Crossover Portion – Safety Analysis Set – Subjects Who Are Randomized to Vorinostat and Crossed Over to KW-0761

Table 14.3.2.2	Number (%) of Subjects with Treatment-Emergent Adverse Events (TEAEs) Related to KW-0761 During Crossover Portion – By System Organ Class and Preferred Term – Safety Analysis Set – Subjects Who Are Randomized to Vorinostat and Crossed Over to KW-0761
Table 14.3.2.3	Number (%) of Subjects with Treatment-Emergent Adverse Events (TEAEs) Related to KW-0761 During Crossover Portion – By System Organ Class, Preferred Term, and Highest CTCAE Grade – Safety Analysis Set – Subjects Who Are Randomized to Vorinostat and Crossed Over to KW-0761
Table 14.3.2.4	Number (%) of Subjects with Grade III/IV/V Treatment-Emergent Adverse Events (TEAEs) Related to KW-0761 During Crossover Portion – By System Organ Class and Preferred Term – Safety Analysis Set – Subjects Who Are Randomized to Vorinostat and Crossed Over to KW-0761
Table 14.3.2.5	Number (%) of Subjects with Treatment-Emergent Serious Adverse Events Related to KW-0761 During Crossover Portion – By System Organ Class and Preferred Term – Safety Analysis Set – Subjects Who Are Randomized to Vorinostat and Crossed Over to KW-0761
Table 14.3.2.6	Number (%) of Subjects with Treatment-Emergent Adverse Events (TEAEs) Related to KW-0761 Leading to Discontinuation During Crossover Portion – By System Organ Class and Preferred Term – Safety Analysis Set – Subjects Who Are Randomized to Vorinostat and Crossed Over to KW-0761
Table 14.3.3.1	Number(%) of Subjects with Treatment-Emergent Adverse Events (TEAEs) Related to KW-0761 for Subjects Exposed to KW-0761 - By System Organ Class and Preferred Term - Safety Analysis Set
Table 14.3.3.2	Exposure-Adjusted Incidence Rate of Infections and Infestations During Randomized Treatment Period - By Preferred Term - Safety Analysis Set
Table 14.3.3.3	Exposure-Adjusted Event Rate of Infections and Infestations During Randomized Treatment Period - By Preferred Term - Safety Analysis Set
Table 14.3.3.4	Exposure-Adjusted Incidence Rate of Respiratory, Thoracic and Mediastinal Disorders During Randomized Treatment Period - By Preferred Term - Safety Analysis Set

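### No all-causality table by system organ class and preferred term is planned for the crossover portion or for all KW-0761-exposed subjects pooled

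*SAP*

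**What the plan says.** Protocol 10.2 describes the crossover group's safety reporting by onset date: "AEs with an onset date/time after the first dose of KW-0761 will be summarized separately within that KW-0761 crossover group". The same section says of treatment-emergent events (TEAEs) in general: "Treatment-emergent AEs will be grouped and tabulated by MedDRA preferred terms and system organ class". Neither sentence is limited by causality.

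SAP 6.12.1 starts in the same way. It defines the crossover events by timing ("TEAEs during the crossover portion are defined as adverse events with an onset date/time after the first dose of KW-0761", with an end point of 90 days after the last dose or the start of another therapy) and then says "TEAEs during the crossover portion will be summarized separately". Later in the section the rule narrows: "Adverse events during the crossover portion that are related to KW-0761 will be summarized separately". The only further crossover summary mentioned there is an optional one of vorinostat-related events, which is also filtered on causality.

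The table list and shells follow the narrower rule. Tables 14.3.2.2 and 14.3.2.3 begin "Number (%) of Subjects with Treatment-Emergent Adverse Events (TEAEs) Related to KW-0761 During Crossover Portion". Tables 14.3.2.4 to 14.3.2.6 and the pooled exposure Table 14.3.3.1 carry the same restriction in their titles.

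Two other rules in SAP 6.12.1 decide where events land. An event starting after KW-0761 begins "will also be considered as a TEAE during the randomized treatment period if it is considered related to vorinostat". An event with no recorded relationship is treated as probably related.

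**The concern.** The SAP contains two rules for one group, and the tables implement the one that departs from the protocol. SAP Section 1 says the SAP supersedes the protocol's statistical considerations, but also that substantial differences will be identified. Neither 6.12.1 nor the Summary of Revisions identifies this one. Crossover laboratory data and vital signs (SAP 6.12.2 and 6.12.3) are summarized with no relatedness filter, so the adverse-event tables are the exception.

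What is at stake is signal detection for KW-0761, whose further safety assessment is a secondary objective. Causality is assigned by unblinded investigators. It is also harder to assign after crossover. Protocol 5.3 sets a minimum of 2 weeks between the drugs and lets it be shortened, while Protocol 7.1 asks for causality to both drugs for 30 days after vorinostat stops. A cluster of events in one SOC, each judged unlikely to be related, is the pattern an all-causality table would show and a related-only table would not.

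**Working it through.** The plan gives no figure to reproduce, so the check is to classify each planned crossover output and then trace each kind of event through the tables.

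**Step 1. SOC/preferred-term tables, randomized period against crossover.**

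| Content | Randomized, all-causality | Randomized, drug-related | Crossover, all-causality | Crossover, KW-0761-related |
|---|---|---|---|---|
| Overall | 14.3.1.2 | 14.3.1.3 | none | 14.3.2.2 |
| By highest grade | 14.3.1.4 | 14.3.1.5 | none | 14.3.2.3 |
| Grade III/IV/V | 14.3.1.6 | 14.3.1.7 | none | 14.3.2.4 |
| Serious | 14.3.1.8 | 14.3.1.9 | none | 14.3.2.5 |
| Leading to discontinuation | 14.3.1.10 | 14.3.1.11 | none | 14.3.2.6 |

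The pooled Table 14.3.3.1 is also related-only. So 5 of 5 crossover tables plus 1 of 1 pooled table are filtered, and 0 of 6 is all-causality. The randomized period has both versions of each of the five. The exposure-adjusted tables (14.3.3.2 to 14.3.3.9) cover the randomized period only and do not fill the gap.

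**Step 2. Where all-causality crossover events do appear.** Table 14.3.2.1, the crossover overview, has no relatedness limit in its title. It takes the layout of Table 14.3.1.1, with rows for any AE, any TEAE, Grade III/IV/V events, deaths, serious events and discontinuations. It gives subject counts but no terms. Listings 16.2.7.6 to 16.2.7.10 show crossover events subject by subject, with term, grade, seriousness and relationship to each drug. They give no incidence.

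**Step 3. Trace a post-crossover event by attribution.**

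| Investigator's judgement | SOC/preferred-term table reached |
|---|---|
| Related to KW-0761 | Crossover 14.3.2.x and pooled 14.3.3.1 |
| Related to vorinostat only | Randomized-period tables, vorinostat column |
| Related to both | Both of the above |
| Relationship not recorded | Treated as related |
| Unlikely or not related to both | None |

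Only the last row is absent from every SOC/preferred-term table. Possibly related counts as related, so the row holds only events put in the two lowest causality categories for both drugs.

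**Step 4. Internal consistency of Table 14.3.3.1.** Its title limits it to KW-0761-related events. Its footnote for the crossover and pooled columns says that the crossover TEAEs are what is summarized, with no such limit. A programmer could follow either.

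**The case against.** The strongest case against is that nothing is withheld. The overview gives all-causality counts, including deaths and serious events, and the listings show each event with its term and relationship. A reader might infer from the filter that all-causality crossover events are never tabulated. Table 14.3.2.1 shows that this is not so.

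A reader might also infer that the crossover group cannot be compared with the randomized arms. That does not hold either. The drug-related randomized tables match the crossover tables one for one, Table 14.3.3.1 puts randomized and crossover KW-0761 subjects in adjacent columns on the same related basis, and the two overviews match on all causes. Only an all-causality comparison by SOC and preferred term is missing.

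It is also tempting to put a percentage on the lost events by assuming a proportion judged related and taking the complement. The documents give no such proportion. The complement would also be too large whenever some of the remaining events are attributed to vorinostat, since those are tabulated elsewhere. Nor do the documents say how many subjects cross over, so the added exposure cannot be stated as large.

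The crossover sentence in Protocol 10.2 does not itself specify SOC and preferred term, so the overview is arguably a separate summary. The section's general TEAE sentence does specify them, and the SAP's two statements differ whatever the protocol requires. Finally, a related-only table has a use: it helps to separate the drugs in the 30-day window. That is a reason to keep it, not a reason to omit the all-causality version.

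**Conclusion.** The point holds as a gap in aggregate safety reporting. None of the six SOC/preferred-term tables for the crossover portion or pooled KW-0761 exposure is all-causality. Post-crossover events judged unlikely or not related to both drugs, including serious ones and those leading to discontinuation, are seen only as counts without terms and in listings. This follows from a stated SAP rule that conflicts with another sentence of the same section and with Protocol 10.2, and the SAP does not declare the difference.

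The size can be given in tables but not in events. The conclusion assumes that Table 14.3.2.1 is produced as its title and layout indicate. If the relatedness sentence were applied to it literally, the gap would be wider. Subjects randomized to KW-0761 have full all-causality tables. The primary analysis and the randomized safety comparison are unaffected. The change should be made because KW-0761 safety is a stated objective in an open-label trial.

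**What to change.** Add all-causality versions of Tables 14.3.2.2 to 14.3.2.6 and of Table 14.3.3.1, and keep the KW-0761-related versions beside them. In SAP 6.12.1, reconcile the sentence that promises a summary of crossover TEAEs with the one that restricts it to related events. Make the title and footnote of Table 14.3.3.1 agree, and state that Table 14.3.2.1 covers all causes. If the restriction is kept for any table, declare it as a departure from Protocol 10.2, as SAP Section 1 requires.

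The all-causality shells already exist for the randomized period and the events are already in the listings. The cost is a few more tables and a small text change. No new data are needed and no efficacy analysis changes.
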